### **Symptom improvement rate**

The symptom improvement rate will be defined as the number (%) of patients with 2 consecutive assessments at least 14 days apart that show a clinically meaningful improvement (a decrease from baseline score  $\geq 10$  for EORTC QLQ-C30 symptom scales) in that symptom from baseline. The denominator will consist of a subset of the FAS who have a baseline symptom score  $\geq 10$ .

### **HRQoL/function improvement rate**

The HRQoL/function improvement rate will be defined as the number (%) of patients with 2 consecutive assessments at least 14 days apart that show a clinically meaningful improvement (an increase from baseline score  $\geq 10$  for EORTC QLQ-C30 functional scales and global health status/QoL) in that scale from baseline. The denominator will consist of a subset of the FAS who have a baseline HRQoL/function score  $\leq 90$ .

### **PRO Compliance**

Summary measures of overall compliance and compliance over time will be derived for the EORTC QLQ-C30. These will be based upon:

- Received forms=number of EORTC QLQ-C30 forms
- Expected forms= number of patients still under HRQL follow-up at the specified assessment time excluding patients in countries with no available translation. For patients that have progressed, the latest of progression and safety follow-up will be used to assess whether the patient is still under HRQL follow-up at the specified assessment time. Date of study discontinuation will be mapped to the nearest visit date to define the number of expected forms.

- Evaluable forms = subset of the expected EORTC QLQ-C30 forms with at least one subscale that can be determined.
- Compliance rate =  $\text{Evaluable/Expected} \times 100$
- Evaluability rate =  $\text{Evaluable/Received} \times 100$

Thus the overall compliance rate is defined as number of patients with an evaluable baseline and at least one evaluable follow-up form (as defined above), divided by the number of patients expected to have completed at least a baseline EORTC QLQ-C30 form.

Compliance over time will be calculated separately for each visit, including baseline, as the number of patients with an evaluable baseline form and a form at the time point (as defined above), divided by number of patients still expected to complete forms at that visit. Similarly the evaluability rate over time will be calculated separately for each visit, including baseline, as the number of evaluable forms (per definition above), divided by the number of received forms.

### 3.4.2 EORTC QLQ-H&N35

The H&N35 is a head and neck cancer-specific module from the EORTC for head and neck cancer comprising 35 questions to assess head and neck cancer symptoms. The head and neck cancer module includes 11 single items and 7 multi-item scales that assess pain, swallowing, senses (taste and smell), speech, social eating, social contact, and sexuality. For all items and scales, high scores indicate increased symptomatology/more problems.

The scoring approach for the H&N35 is identical in principle to that for the symptom scales/single items of the EORTC QLQ-C30. As the wording is reversed on the H&N35, higher scores represent greater symptom severity.

#### Definition of clinically meaningful changes

Changes in score compared with baseline will be evaluated. The developers of the H&N35 have suggested that a minimum clinically meaningful change is a change in the score from baseline of  $\geq 10$  for scales/items from the H&N35 module (Bjordal et al 2000). For example, a clinically meaningful deterioration or worsening in dry mouth (as assessed by H&N35) is defined as an increase in the score from baseline of  $\geq 10$ . At each post-baseline assessment, the change in symptoms/functioning from baseline will be categorized as improved, no change, or deterioration, as shown in Table 11. CCI

**Table 11 Change from BL and visit response for EORTC QLQ H&N35**

Score	Change from baseline	Visit response
H&N35 symptom scales and items	$\geq +10$	Deterioration
	$\leq -10$	Improvement
	Otherwise	No change

HRQoL Health-related quality of life; H&N35 35-item head and neck quality of life questionnaire.

### Time to symptom deterioration

For each of the symptom scales/items in the H&N35, time to symptom deterioration will be defined as the time from randomization until the date of the first clinically meaningful symptom deterioration (an increase in the score from baseline of  $\geq 10$ ) or death (by any cause) in the absence of a clinically meaningful symptom deterioration, regardless of whether the patient withdraws from study treatment or receives another anticancer therapy prior to symptom deterioration. Death will be included as an event only if the death occurs within 2 visits of the last PRO assessment where the symptom change could be evaluated.

Patients whose symptoms (as measured by the H&N35) have not shown a clinically meaningful deterioration and who are alive at the time of the analysis will be censored at the time of their last PRO assessment where the symptom could be evaluated. Also, if symptoms progress after 2 or more missed PRO assessment visits or the patient dies after 2 or more missed PRO assessment visits, the patient will be censored at the time of the last PRO assessment where the symptom could be evaluated. If a patient has no evaluable visits or does not have baseline data, they will be censored at 0 days. The population for analysis of time to symptom deterioration will include a subset of the FAS population who has baseline scores  $\leq 90$ .

### Symptom improvement rate

The symptom improvement rate will be defined as the number (%) of patients with 2 consecutive assessments at least 14 days apart that show a clinically meaningful improvement (a decrease from baseline score  $\geq 10$  for H&N35 scales/items) in that symptom from baseline. The denominator will consist of a subset of the FAS who have a baseline symptom score  $\geq 10$ .

### PRO Compliance

Summary measures of overall compliance and compliance over time will be derived for the EORTC QLQ-H&N35. These will be based upon the compliance derivation described for EORTC QLQ-C30

#### 3.4.3

CCI [Redacted]

CCI [Redacted]

CCI [Redacted]

3.4.4 CCI [Redacted]

CCI [Redacted]

3.4.5 CCI [Redacted]

CCI [Redacted]

3.4.6 CCI [Redacted]

CCI [Redacted]

### **3.5 Pharmacokinetics and Immunogenicity Variables**

Analyses to evaluate the pharmacokinetics of MEDI4736 monotherapy, and MEDI4736 + tremelimumab combination therapy and to investigate the immunogenicity of MEDI4736 and tremelimumab will be performed by a designated third party on behalf of AstraZeneca.

#### **3.5.1 Population of pharmacokinetics and exposure-response/safety analysis**

A population PK model may be developed using a non-linear mixed-effects modelling approach for MEDI4736 monotherapy and for MEDI4736 in combination with tremelimumab. The impact of physiologically-relevant patient characteristics (covariates) and disease on PK of both agents may be evaluated. The relationship between MEDI4736 PK exposure or tremelimumab PK exposure and the effect on safety and efficacy endpoints may be evaluated. The results of such an analyses, if conducted, will be reported outside of the CSR.

#### **3.5.2 Pharmacokinetic analysis**

Pharmacokinetic data analyses of MEDI4736 and tremelimumab will be performed by the MedImmune Global Pharmacokinetics Pharmacodynamics (PK-PD) & Bioanalysis group or designee. No formal non-compartmental (NCA) PK analysis will be conducted due to the sparse PK sampling scheme for MEDI4736 and tremelimumab, which does not allow for meaningful determination of PK parameters.

MEDI4736 and tremelimumab concentration data and summary statistics will be tabulated by treatment arm and visit. PK parameters, such as peak and trough concentration of MEDI4736 and tremelimumab, will be derived from raw data measurements as data allow.

For data below limit of quantification (BLQ) the following rules will apply:

- If, at a given time point, 50% or less of the serum concentrations are not quantifiable (NQ), the geometric mean, CV%, geometric CV%, mean and SD will be calculated by substituting the limit of quantification (LOQ) for values which are NQ.
- If more than 50%, but not all, of the concentrations are NQ, the geometric mean, CV%, geometric CV%, mean and SD will be reported as not calculable (NC).
- If all the concentrations are NQ, the geometric mean and mean will be reported as NQ and the CV%, geometric CV% and SD as NC.

ALQ results of the PK assay will be excluded from summary statistics calculations.

If two results are obtained for one PK sample, the following rules will be applied:

- If the results are  $\leq \pm 30\%$  of each other (by calculating the relative percent difference (RPD)), then the mean of the two results will be reported

- If the results are  $> \pm 30\%$  of each other (RPD), then this will be reported as NRR (No Reportable Result)
- If one result is BLQ and one  $>$  lower limit of quantification (LLOQ), this will be reported as NRR

The RPD will be calculated using the following formula:

$$RPD (\%) = \frac{Result\ 1 - Result\ 2}{Mean\ of\ Results\ 1\ and\ 2} \times 100$$

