^g Pre-dose (within 60 minutes prior to start of infusion). For patients in the MEDI4736 + tremelimumab combination therapy arm: pre-dose samples for both MEDI4736 and tremelimumab can be taken within 60 minutes prior to the start of the tremelimumab infusion.

^h Within 10 minutes of the end of infusion.

ⁱ If screening assessments are performed within 3 days prior to Day 1 (first infusion day), they do not need to be repeated at Day 1.

^j Free T₃ or free T₄ will only be measured if TSH is abnormal or if there is clinical suspicion of an AE related to the endocrine system.

^k For women of childbearing potential only. A pregnancy test must be performed within 7 days before Cycle 1 Day 1. A urine or serum pregnancy test is acceptable.

^l Results for electrolytes, full blood count, and liver function tests must be available before commencing an infusion (within 3 days).

^m During the combination portion of treatment, tremelimumab will be administered first; the MEDI4736 infusion will start approximately 1 hour (maximum 2 hours) after the end of the tremelimumab infusion. If there are no clinically significant infusion reactions with the first cycle, then for all other cycles, MEDI4736 can be given immediately after the tremelimumab infusion has finished.

ⁿ Patients will complete PROs using handheld devices at home.

^o CCI

^p MEDI4736 + tremelimumab combination therapy only: The collection of tumor biopsies at the time of progression prior to retreatment is mandated; the Investigator must consult with the Study Physician if such sampling is not feasible.

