## LIST OF ABBREVIATIONS

Abbreviation or special term	Explanation
ADA	Antidrug antibody
AE	Adverse event
AEPI	Adverse events of possible interest
AESI	Adverse events of special interest
ALT	Alanine aminotransferase
ALQ	Above Limit of Quantification of PK assay
APF6	Proportion of patients alive and progression free at 6 months from randomization
APF12	Proportion of patients alive and progression free at 12 months from randomization
AST	Aspartate aminotransferase
Baseline	Refers to the last assessment prior to intake of the first dose of IP, except for Efficacy where baseline refers to the last visit prior to enrollment.
BICR	Blinded Independent Central Review
BLQ	Below Limit of Quantification of PK assay
BMI	Body Mass Index
BoR	Best objective response
CI	Confidence interval
COVID-19	Coronavirus Disease 2019
CR	Complete response
CRA	Clinical Research Associate
CRF / eCRF	Case Report Form (electronic)
CSP	Clinical Study Protocol
CSR	Clinical Study Report
CT	Computed tomography
CTCAE	Common Terminology Criteria for Adverse Event
ctDNA	Circulating tumor DNA
CTLA-4	Cytotoxic T-lymphocyte-associated antigen 4
CTM	Clinical team manager
CTMS	Clinical trial management system
DCO	Data cut-off
DCR	Disease control rate
DoR	Duration of response

Abbreviation or special term	Explanation
ECG	Electrocardiogram
ECOG	Eastern Cooperative Oncology Group
EDoR	Expected Duration of Response
EM	Early mortality
EORTC	European Organisation for Research and Treatment of Cancer
CCI	CCI
FAS	Full analysis set
HLT	High level term
HLGT	High level group term
HR	Hazard ratio
CCI	CCI
HRQoL	Health-related quality of life
IC	Tumor-associated immune cell
IDMC	Independent Data Monitoring Committee
ICR	Independent Central Reviewer
imAE	Immune-mediated Adverse Events
IMT	Immunomodulatory therapy
IP	Investigational product
irRECIST	Immune-related response criteria
ITT	Intent-to-treat
IV	Intravenous
KM	Kaplan-Meier
LLOQ	Lower Limit of Quantification of PK assay
MD	Medical doctor
MedDRA	Medical Dictionary for Regulatory Activities
MEDI4736	Immune-mediated therapy
mg	Milli-gram
MMA	Medical monitoring associate
MRI	Magnetic resonance imaging
MMRM	Mixed effect model repeat measurement
NA	Not applicable
NCI	National Cancer Institute

Abbreviation or special term	Explanation
NE	Not evaluable
NED	No evidence of disease
CCI	CCI
NRR	No Reportable Result
NTL	Non-target lesions
ORR	Objective response rate
OS	Overall survival

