
To assess the efficacy of MEDI4736 + tremelimumab combination therapy compared to MEDI4736 monotherapy in terms of PFS, ORR, and OS
	
PFS and ORR using site investigator assessments according to RECIST 1.1 in the PD-L1 TC/IC high subgroup, low risk of early mortality (EM) subgroup, ctDNA TMB high subgroup (<math>\geq 16</math> mut/Mb) and all-comers
 
OS in the PD-L1 TC/IC high subgroup, low risk of early mortality (EM) subgroup, ctDNA TMB high subgroup (<math>\geq 16</math> mut/Mb) and all-comers

To assess disease-related symptoms and health-related quality of life in patients treated in patients treated with MEDI4736 + tremelimumab combination therapy and MEDI4736 monotherapy compared to SoC (EXTREME) using the EORTC QLQ-C30 v3 and the QLQ-H&N35 module
	
EORTC QLQ-C30: global health QoL, functioning (physical) and symptoms (fatigue in the PD-L1 TC/IC high subgroup and all-comers
 
EORTC QLQ-H&N35: symptoms (pain, swallowing) in the PD-L1 TC/IC high subgroup and all-comers
 
Changes in WHO/ECOG performance status in the PD-L1 TC/IC high subgroup and all-comers

To assess the PK of MEDI4736 + tremelimumab combination therapy and MEDI4736 monotherapy
	
Concentration of MEDI4736 and tremelimumab in blood and PK parameters, such as peak concentration and trough (as data allow; sparse sampling)

To investigate the immunogenicity of MEDI4736 and tremelimumab
	
Presence of ADAs for MEDI4736 and tremelimumab

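### If any end-of-infusion PK samples are reported above the assay range, leaving them out of the summary statistics would understate peak concentration and its spread

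*SAP*

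**What the plan says.** The SAP list of abbreviations defines ALQ as "Above Limit of Quantification of PK assay". Section 3.5.2 then states that "ALQ results of the PK assay will be excluded from summary statistics calculations". No substitution, count or threshold accompanies this sentence. The July 2018 entry in the SAP amendment history records that the rule was added on purpose.

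The same section treats the lower end differently. When half or fewer of the concentrations at a time point are not quantifiable, the mean, geometric mean, SD and CVs are obtained by "substituting the limit of quantification (LOQ) for values which are NQ". When more than half but not all are affected, these statistics are declared not calculable. When all are affected, the mean and geometric mean are reported as not quantifiable.

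Peak concentration is named in the secondary PK objective (SAP Table 2; Protocol section 2.2), subject to what sparse sampling allows. There is no non-compartmental analysis. Section 3.5.2 says "PK parameters, such as peak and trough concentration of MEDI4736 and tremelimumab, will be derived from raw data measurements as data allow". The samples that measure the peak are those in Protocol Table 2 taken "Within 10 minutes of the end of infusion", at Cycles 1 and 4.

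**The concern.** An above-range result is not uninformative. With a common upper limit, it is known to exceed every quantified result at that time point. Dropping it truncates the upper tail, so the mean, geometric mean, SD and CV of what remains are all too low. Any such results would be expected mainly among the end-of-infusion samples, which are the ones that measure the peak.

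The rule also has no stopping point. If most peak samples at a visit were above range, the SAP would still report a mean, computed from the lowest minority. The below-limit rule avoids the equivalent problem at the other end by declaring the mean not calculable.

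At stake is the description of peak exposure and its variability in the clinical study report. Population PK modelling is optional and would be reported elsewhere (SAP section 3.5.1), so these tables may be the report's only PK summary.

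**Working it through.** The plan states no PK figure to reproduce. The check is of the direction and possible size of the bias.

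**Inputs from the documents.** Above-range results are excluded, and below-range results are set to the limit when 50% or fewer are affected (SAP 3.5.2). Peak samples are taken at the end of infusion (Protocol Table 2). The upper limit, any dilution and re-assay rule, and the expected share above range are not given. Protocol section 5.4.1 defers the assay details to a separate validation report.

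**Assumptions.** Peak concentration is lognormal with 35% CV, and a share q lies above a common upper limit. The median is scaled to 1. Then s = √ln(1 + 0.35²) = 0.340, u = z(1−q), and the upper limit is U = exp(su).

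**Geometric mean relative to the truth.**
- Exclusion: exp[−s·φ(u)/(1−q)]
- Substitution at U: exp[s·(q·u − φ(u))]

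At q = 5%, u = 1.645 and φ(u) = 0.1031. Exclusion gives exp(−0.340 × 0.1031/0.95) = 0.964, a fall of 3.6%. Substitution gives exp[0.340 × (0.0822 − 0.1031)] = 0.993, a fall of 0.7%.

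**Arithmetic mean and SD.** Let A = e^(s²/2)·Φ(u−s) and B = e^(2s²)·Φ(u−2s).
- Exclusion: mean A/(1−q), variance B/(1−q) − [A/(1−q)]²
- Substitution: mean A + qU, variance B + qU² − (A + qU)²

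At q = 5%, the true mean is 1.0595 and the true SD is 0.35 × 1.0595 = 0.371. A = 0.958, B = 1.049 and U = 1.749. The SD is 0.297 under exclusion (20% low) and 0.331 under substitution (11% low).

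Falls relative to the truth, in %:

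| Share above range | Geometric mean, excluded | Geometric mean, set to U | Mean, excluded | Mean, set to U | SD, excluded | SD, set to U |
|---|---|---|---|---|---|---|
| 0% | 0 | 0 | 0 | 0 | 0 | 0 |
| 1% | 0.9 | 0.1 | 1.4 | 0.3 | 8 | 3 |
| 2% | 1.7 | 0.2 | 2.4 | 0.5 | 12 | 5 |
| 5% | 3.6 | 0.7 | 4.8 | 1.3 | 20 | 11 |
| 10% | 6.4 | 1.6 | 8.1 | 2.7 | 29 | 18 |
| 20% | 11.2 | 3.7 | 13.5 | 5.7 | 40 | 31 |

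**Sensitivity to the CV.** For CVs from 30% to 80%, the arithmetic mean falls by 4.0% to 13.0% under exclusion with 5% above range, against 1.1% to 4.9% with substitution. With 10% above range the falls are 6.8% to 20.2% against 2.2% to 8.9%.

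**Median.** Under exclusion the median also shifts, to exp[s·z(0.5(1−q))]. At q = 5% this is exp(−0.340 × 0.0627) = 0.979, which is 2.1% low. If above-range values are retained, the median is unaffected while fewer than half are above range.

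**The case against.** The strongest reply is that nothing may happen. If over-range samples are diluted and re-assayed until quantified, few or none will finally be reported as above range, and the bias disappears. The documents neither confirm nor exclude this. This part stands. A reader might infer from the rule that reported peak means are biased, but the documents support only a conditional statement, and the shares and CV used above are assumptions.

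Other stronger readings also fail:
- That the data are lost. The rule concerns summary statistics only. SAP section 4.2.15 still lists concentrations for each patient and dosing day.
- That the SAP contradicts itself. Section 3.3.7 sets values reported as greater than x to x, but it does so for safety assessments. The below-limit rule chiefly affects troughs and adds essentially nothing to any bias in the peak. These are useful precedents, not conflicting instructions.
- That substitution cures the problem. It still lowers the SD by 5% to 31% for shares of 2% to 20%, against 12% to 40% under exclusion. Most of the understated variability remains.
- That trial conclusions are at risk. PK is descriptive, sampling is sparse, and formal testing is confined to OS.

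It can also be said that SAP section 4.1 already calls for the number of observations and the median. But the exclusion applies to that median as well, and a count of observations does not separate above-range samples from missing ones.

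**Conclusion.** The concern holds conditionally. If any end-of-infusion sample is finally reported above the upper limit, the stated rule lowers the reported mean, geometric mean and SD of peak concentration. The direction follows from the rule, given a common upper limit. The size is unknown and may be zero. With a lognormal peak, 35% CV and up to 20% of samples above range, the geometric mean is understated by at most 11.2%, against 3.7% with substitution. The improvement in the mean and geometric mean holds at every non-zero share examined. The improvement in the SD is real but partial. This is a minor point about a descriptive secondary outcome, worth making because the correction costs almost nothing.

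**What to change.** Replace the sentence in SAP section 3.5.2 with a rule that mirrors the one for below-limit results:

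- When 50% or fewer of the results at a time point are above range, set them to the upper limit of quantification. When more than 50% are, report the mean, geometric mean, SD and CVs as not calculable.
- Report the number and percentage of above-range results at each time point.
- Present the median and quartiles with above-range values retained at the top of the ranking. The upper quartile is known only while fewer than a quarter are above range; otherwise show it as exceeding the limit.

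A statement of whether above-range samples are diluted and re-assayed would tell readers whether the rule is likely to be used.

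The cost is one rewritten sentence and a few extra table rows, with no new data. The downside is that wherever a value is substituted, the mean and SD remain understated and must be flagged. If a time point also has below-limit values raised to the lower limit, its mean is not a strict lower bound.

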### 3.5.3 Immunogenicity analysis

Serum samples for ADA assessments will be conducted utilizing a tiered approach (screen, confirm, titer), and ADA data will be collected at scheduled visits shown in the CSP. ADA result from each sample will be reported as either positive or negative. If the sample is positive, the ADA titer will be reported as well. In addition, the presence of neutralizing antibody (nAb) will be tested for all ADA positive samples using a ligand-binding assay. The nAb results will be reported as positive or negative. A patient is defined as being ADA-positive if a positive ADA result is available at any time, including baseline and all post-baseline measurements; otherwise ADA negative.

The number and percentage of patients who develop detectable ADA to MEDI4736 or tremelimumab will be determined for each of the following categories for each treatment group. The denominator for percentage calculations is the number of ADA-evaluable patients in the treatment group.

- ADA positive at any visit, baseline and/or post-baseline. The percentage is known as ADA prevalence.
- ADA positive post-baseline and positive at baseline
- ADA positive post-baseline and not detected at baseline (treatment-induced ADA positive)
- ADA not detected post-baseline and positive at baseline
- Baseline ADA titer that was boosted by  $\geq 4$ -fold following drug administration (treatment-boosted ADA positive)
- Treatment-emergent ADA positive, defined as the sum of treatment-induced ADA positive and treatment-boosted ADA positive. The percentage is known as ADA incidence.
- Persistently positive ADA, defined as having at least 2 post-baseline ADA positive measurements with at least 16 weeks (112 days) between the first and last positive measurements, or an ADA positive result at the last available assessment
- Transiently positive ADA, defined as having at least one post-baseline ADA positive measurement and not fulfilling the conditions for persistently positive
- nAb positive at baseline and/or post-baseline

